1.1 Study design

The study design is shown in [Figure 1-1](#) and [Figure 1-2](#).

This is an interventional, phase II, single-arm, multicenter, open-label, study to investigate the efficacy and safety of the combination of eltrombopag and cyclosporine in treatment-naïve adult patients with severe aplastic anemia (SAA) as first line therapy administered for 6 months, with an additional 18 months follow-up for responders for cyclosporine tapering and duration of response until relapse or 24 months whichever is earlier.

At 6 months, **responders** will discontinue eltrombopag and start to taper cyclosporine until 24 months. Responders who are no longer responding at 6 months and **non-responders** will discontinue the treatment and study at 6 months and will be followed-up for 30 days. Responders who relapse prior to 24 months will discontinue cyclosporine and study, and will be followed-up for 30 days.

Responders who relapse and non-responders already in the follow-up under the previous protocol version will be discontinued from the study within 30 days of the approval of the protocol amendment.

The lack of availability of anti-thymocyte globulin (ATG) in several countries has left a large proportion of patients with SAA with limited treatment options and poor outcome. In this context, the combination of cyclosporine and eltrombopag, 2 therapies with different modes of action, is an attractive therapeutic option to address this unmet medical need. Cyclosporine acts as an immunosuppressant and eltrombopag acts as a stimulator of bone marrow progenitor cells.

Fifty (50) patients are planned to be enrolled.

Figure 1-1 Study design under protocol amendment 1

Under protocol amendment (PA) 1 (4 phases: Treatment 1; Treatment 2; Follow-up; post-treatment follow-up)

[figure not shown]
[figure not shown]

Figure 1-2 Study design under protocol amendment 2

Under PA2 (2 phases: Treatment 1 and Treatment 2)

* Follow-up for duration of response until relapse or Month 24 whichever is earlier for responders only who did not relapse prior to Month 6

1.2 Study objectives and endpoints

Table 1-1 displays the study objectives and endpoints.

Table 1-1 Objectives and related endpoints

Objective	Endpoint
Primary	
To evaluate the efficacy of eltrombopag + cyclosporine as first-line therapy on overall hematologic response (partial and complete response) by 6 months	Overall hematologic response (CR + PR)* rate by 6 months (definition of CR and PR is given as footnote below)

Objective	Endpoint
Secondary	
1. Evaluate the effect of eltrombopag + cyclosporine on overall hematologic response (partial and complete response): • by 3 months • at 12 months • at 24 months	Overall hematologic response (CR + PR)* rate: • by 3 months • at 12 months • at 24 months
The following secondary objectives will be assessed by 6 months and 24 months (responders only) as appropriate and will be reported in a cumulative basis until the cutoff date (LPLV for final analysis)	
2. To evaluate the duration of hematologic response	Time from the date of the first response to the date of first relapse (defined as no longer meeting definition of PR (and not CR))
3. To evaluate the proportion of patients who relapse	Percentage of patients who relapse
4. To evaluate the clonal evolution to myelodysplasia, paroxysmal nocturnal hemoglobinuria (PNH), and leukemia	Percentage of patients with evolution to myelodysplasia, PNH, and acute leukemia occurring at any time during the study
5. To evaluate red blood cells (RBC) transfusion independence	Percentage of patients who are RBC transfusion independent at least once by 6 months and by 24 months. Independence defined as no RBC transfusion for at least 56 days
6. To evaluate platelet transfusion independence	Percentage of patients who are platelet transfusion independent at least once by 6 months and by 24 months. Independence defined as no platelet transfusion for at least 28 days
7. To evaluate the longest interval without a platelet and RBC transfusion	Duration of longest interval without a platelet transfusion by 6 months and 24 months Duration of longest interval with a RBC transfusion by 6 months and by 24 months
8. To evaluate the effect of Eltrombopag and cyclosporine on patient symptoms and health related quality of life	Change in scores from baseline to 6 months and 24 months on the FACT-G, FACT-TH18, and FACIT-Fatigue scales
9. To evaluate the safety and tolerability of eltrombopag + cyclosporine	Safety will be assessed by: • Frequency and severity of AEs, serious AEs (SAEs) based on the Common Terminology Criteria of Adverse Events (CTCAE version 4.03), and AEs leading to discontinuation, and evaluating changes in laboratory values within 6 months and within 24 months (responders only) • Incidence of adverse events of special interest
10. To characterize the PK of eltrombopag when combined to cyclosporine	Plasma PK parameters of eltrombopag at 2 weeks and trough concentrations at 1 month, 2 months, 3 month, and 6 months

Objective	Endpoint

*Overall hematologic response = patients with complete response (CR) + patients with partial response (PR)

a. Partial response is defined as any two of the following parameters at two consecutive, scheduled visit measurements at least 7 days apart during the study (and not sufficient for CR) and no platelet transfusions within 7 days of platelet measurement (can still be a responder if ANC and reticulocyte measurements are valid):

- Absolute neutrophil count (ANC) $\geq 500/\mu\text{L}$
- Platelet count $\geq 20\,000/\mu\text{L}$
- Reticulocyte count $\geq 60\,000/\mu\text{L}$ (automated)

b. Complete response is defined as all three parameters meet the following criteria at two consecutive, scheduled visit measurements at least 7 days apart during the study and no platelet transfusions within 7 days of platelet measurement and no RBC transfusion with 14 days of the hemoglobin measurements:

- Absolute neutrophil count (ANC) $\geq 1\,000/\mu\text{L}$
- Platelet count $\geq 100\,000/\mu\text{L}$
- Hemoglobin $\geq 10\text{g/dL}$

Example: At the end of 6 months out of 50 patients enrolled, if 13 patients satisfy the criteria for CR and 3 patients satisfy the criteria for PR, the overall hematologic response will be $13+3=16$ patients.

2 Statistical methods

2.1 Data analysis general information

2.1.1 Data included in the analysis

Statistical analyses will be performed using all data collected in the database up to the respective data cut-off dates (last patient last visit (LPLV) for the final analysis). All data with an assessment date or event start date (e.g. vital sign assessment date or start date of an adverse event (AE)) prior to or on the cut-off date will be included in the analysis. Any data collected beyond the cut-off date will not be included in the analysis and will not be used for any derivations.

All events with start date before or on the cut-off date and end date after the cut-off date or missing will be reported as 'ongoing'. For these events, the end date will show as missing in the listings however the earliest of; death date, last contact date or cutoff date will be used in derivations of endpoints as appropriate.

Withdrawal of Informed Consent

Any data collected in the clinical database after a patient withdraws informed consent from all further participation in the trial, will not be included in the analysis. The date on which a patient withdraws full study consent is recorded in the electronic case report form (eCRF).

2.1.2 General analysis conventions

Data from all study centers will be pooled for analyses.

Qualitative data (e.g., gender, race, etc.) will be summarised by absolute and relative frequencies. A missing category will be included where applicable. Percentages will be calculated using the number of patients in the relevant analysis set or subgroup as the denominator.

Quantitative data (e.g., age, body weight, etc.) will be summarised by appropriate descriptive statistics (i.e. mean, standard deviation (sd), minimum, 25th percentile, median, 75th percentile and maximum).

2.1.3 General definitions

Study drug and study treatment

Study drugs refer to the individual drugs used in the study, eltrombopag or cyclosporine.

Study treatment refers to either eltrombopag or cyclosporine or eltrombopag+cyclosporine.

Date of first administration of study drug

The date of first administration of study drug is derived as the first date when a nonzero dose of study drug is administered. The date of first administration of study drug is also referred to as ***start date of study drug***. Start date of study drug is defined for each study drug. For cyclosporine it is irrespective of capsule or solution form.

Date of last administration of study drug

The date of last administration of study drug is defined as the last date when a nonzero dose of study drug is administered. This date is also referred to as ***last date of study drug***. Last date of study drug is defined for each study drug. For cyclosporine it is irrespective of capsule or solution form.

Date of first administration of study treatment

The date of first administration of study treatment is derived as the first date when a nonzero dose of any component of study treatment is administered.

For example, if the 1st dose of eltrombopag is taken on 08-Feb-2017, and 1st dose of cyclosporine, is taken on 07-Feb-2017, then the date of first administration of study treatment is 07-Feb-2017. The date of first administration of study treatment is also referred to as ***start date of study treatment***.

Date of last administration of study treatment

The date of last administration of study treatment is derived as the last date when a nonzero dose of any component of study treatment is administered.

For example if the last dose of eltrombopag is taken on 08-Aug-2017, and the last dose of cyclosporine is taken on 07-Aug-2017, then the date of last administration of study treatment is on 08-Aug-2017. This date is also referred to as *last date of study treatment*.

Duration of exposure

The duration of exposure for the **study drugs** will be calculated as:

- Duration of study drug exposure (months) = (last date of study drug) – (first date of study drug) + 1.

The duration of exposure for the **study treatment** will be calculated as:

- Duration of study treatment exposure (months) = (last date of study treatment) – (first date of study treatment) + 1.

If the start or end date of a study drug is missing, the duration will be missing. The durations will include periods of temporary interruption (planned or actual) for any reason.

Dose interruption

An interruption is defined as an actual zero dose on one or more days between two non-zero dosing records.

Note: The last zero dose of a study drug (followed by permanent discontinuation) is not considered as a dose interruption. For the purpose of summarizing interruptions and reasons, in case multiple entries for interruption are entered on consecutive days with different reasons these will be counted as separate interruptions. However, if the reason is the same in these multiple entries on consecutive days, then it will be counted as one interruption.

Dose reduction

A dose reduction is where the prescribed dose is lower than the previous prescribed dose or where the actual dose administered/total daily dose is lower than the prescribed dose. Any dose change to correct a dosing error will not be considered a dose reduction, e.g. if due to a dosing error, a patient receives higher than protocol planned starting dose and moves down to the planned starting dose then this is not counted as a reduction, however if they move directly from a higher than planned starting dose down to a lower than protocol planned starting dose, then this is counted as a reduction.

Note: It is assumed that if there is a dose reduction, then the 'Dose changed' box was ticked on the dose administration eCRF page.

Cumulative dose

Cumulative dose of a study treatment is defined as the total dose given during the study treatment exposure and will be summarised for each of the study treatment components (eltrombopag and cyclosporine), respectively.

The **planned cumulative dose** for a study treatment component refers to the total planned dose as per the protocol up to the last date of study drug administration. The planned cumulative dose is not summarised/listed. It is used for relative dose intensity calculations. The **actual cumulative dose** refers to the total actual dose administered, over the duration for which the patient is on the study treatment as documented in the dose administration eCRF.

For continuous dosing, the actual cumulative dose is the sum of the non-zero doses recorded over the dosing period and the planned cumulative dose is the planned starting dose summed over the same dosing period.

For cyclosporine the cumulative dose will be calculated separately for capsules (mg) and solution (mg/ml).

For patients who did not take any drug, the actual cumulative dose is by definition equal to zero for that drug.

Dose intensity and relative dose intensity

Dose intensity (DI) for patients with non-zero duration of exposure is defined as follows:

$\text{DI (dosing unit / unit of time)} = \text{Actual cumulative dose (dosing unit)} / \text{Duration of exposure (unit of time)}$.

e.g. $\text{DI (mg/day)} = (100 \text{ mg/day} * 1050 \text{ days}) / 1080 \text{ days} = 97.2 \text{ mg/day}$

For patients who did not take any drug the DI is by definition equal to zero.

Planned dose intensity (PDI) is the assigned dose by unit of time planned to be given to patients as per protocol in the same dose unit and unit of time as that of the DI, i.e.

$\text{PDI (dosing unit / unit of time)} = \text{Planned cumulative dose (dosing unit)} / \text{Duration of exposure (unit of time)}$.

For Part 2 of the study, note that only cyclosporine is administered and it is with a tapering regime.

For cyclosporine use 10 mg/kg/day as the planned dose for the first record and after that use the “prescribed dose x 2” as the planned dose and the “total daily dose” as the actual dose for exposure calculations. Summarise results in mg/kg/day.

For eltrombopag use 150 mg/day (or 100 mg/day for E/SE Asian patients) for planned dose for all records and “total daily dose” as the actual dose. Summarise results in mg/day.

Relative dose intensity (RDI) is defined as follows:

$\text{RDI} = \text{DI (dosing unit / unit of time)} / \text{PDI (dosing unit / unit of time)}$.

e.g. $\text{RDI} = \text{DI (92.7 mg/day)} / \text{PDI (100 mg/day)} = 0.927$

Study day

The study day describes the relative day of the event related to the start date of study treatment.

The reference start date is designated as **Study Day 1**. Study Day -1 is the day that precedes Day 1. Study Day 0 is not defined. Study day is not to be used in numerical computations, for example in calculating exposure.

The study day will be calculated as:

- The date of the event (visit date, onset date of an event, assessment date etc.) - reference start date + 1, if event is on or after the reference start date.
- The date of the event (visit date, onset date of an event, assessment date etc.) - reference start date, if event precedes the reference start date.

The reference start date for all assessments (safety, efficacy, patient reported outcomes (PROs), etc.) will be the start date of study treatment.

The study day will be displayed in the data listings. If an event starts before the reference start date, the study day displayed in the listing will be negative.

Baseline

Baseline is the result of an investigation describing the “true” uninfluenced state of the patient, defined as the period from the date of signing any informed consent document to the start date of study treatment. Assessments, specified to be collected post-dose on the first date of study treatment are not considered.

The last non-missing assessment, including unscheduled assessments on or before the date of start of study treatment is defined as “baseline value” or “baseline assessment”.

Where multiple measurements meet the baseline definition, with no further flag or label that can identify the chronological order, then values from central assessments should be considered as baseline rather than local values.

For electrocardiogram (ECG) parameters, if there are multiple replicates per time point, the average of these measurements would be calculated for baseline (if not already available in the database).

If patients have no value as defined above, the baseline result will be missing.

Observation periods

The overall observation period will be divided into three mutually exclusive segments:

1. **Pre-treatment:** from day of patient’s informed consent to start date of study treatment
2. **On-treatment:** from start date study treatment to last date of study treatment + 30 days
3. **Post-treatment:** from last date of study treatment + 31 days

On-treatment assessments/events

The definition of on-treatment is given below, depending on the context.

For safety summary tables an on-treatment AE is defined as any AE reported in the following time interval (including the lower and upper limits):

- <date of first administration of study treatment; date of last administration of study treatment + 30 days>

This corresponds to the definition of treatment-emergent AEs given in the protocol, i.e. AEs which are newly reported or worsening from baseline.

An on-treatment assessment is defined as any assessment performed after the date of first administration of study treatment (except for assessments specified to be collected post-dose on that day), i.e. assessments performed in the following time interval (including the lower and upper limits):

- <date of first administration of study treatment + 1; date of last administration of study treatment + 30 days>

For patients whose last date of study treatment is missing, on-treatment assessments/events include any assessment/event present in the database occurring after the start date of study treatment.

Listings will contain all data, flagging assessments/events outside of the on-treatment period where applicable.

Definition of Months and Years

A month will be calculated as $(365.25 / 12) = 30.4375$ days. If duration is to be reported in months, duration in days will be divided by 30.4375. If duration is to be reported in years, duration in days will be divided by 365.25.

Time since initial SAA diagnosis

Time since initial SAA diagnosis (days) = First dose date (Epag/CsA) – date of initial diagnosis.

Time windows

Time windows for assessments are based on protocol specified windows. Weekly and biweekly visits should be completed ± 1 day. Biweekly visits after 6 months should be completed ± 2 days. Monthly visits should be completed ± 3 days. Bimonthly visits should be completed ± 1 week.

Time windows for multiple assessments

In order to summarise data of assessments collected over time (including any unscheduled visits), the assessments will be time slotted. If more than one assessment is done within the same time window, the assessment performed closest to the target date will be used. If 2 assessments within a time window are equidistant from the target date, then the earlier of the 2 assessments will be used. If multiple assessments on the same date then the worst case will be used. The end of treatment assessment will be included if collected within 30 days of the last treatment date. Data from all assessments (scheduled and unscheduled), including multiple assessments, will be listed.

Last contact date

The last contact date will be derived for patients not known to have died at the analysis cut-off date using the latest complete date among the following:

Table 2-1 Last contact date data sources

Source data	Conditions
Date of withdrawal of consent	Withdrawal of study informed consent
Date of discontinuation/phase completion	On the last disposition page completed
Start/End dates from drug administration records	Both study drugs. Doses of 0 are allowed
Sample collection dates	Sample collection marked as 'done' e.g. laboratory or pharmacokinetics (PK)
Assessment dates	At least one non-missing parameter value e.g. vital signs weight value, performance status available etc.
Start/End dates of AEs, medications or surgeries	Non-missing verbatim term

The cut-off date will not be used for last contact date, unless the patient was last seen or contacted on that date. No date post cut-off date will be used. Completely imputed dates (e.g. the analysis cut-off date programmatically imputed to replace the missing end date of a dose administration record) will not be used to derive the last contact date.

The last contact date will be used for censoring of patients in the analysis of duration of hematological response.

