7.1.5 Discontinuation of study treatment

Patients may voluntarily discontinue from the study treatment (eltrombopag and/or cyclosporine) for any reason at any time. If a patient decides to discontinue from the study or fail to return, the investigator should make a reasonable effort (e.g. telephone, e-mail, letter) to understand the primary reason for this decision and record this information in the patient's chart and on the appropriate eCRF pages, see [section 7.1.8](#). They may be considered withdrawn if they state an intention to withdraw, fail to return for visits, or become lost to follow-up for any other reason.

The investigator may discontinue eltrombopag and/or cyclosporine for a given patient if he/she believes that continuation would be detrimental to the patient's well-being.

Patients who discontinue eltrombopag before 6 months, should continue cyclosporine treatment until 6 months (all patients) and until 24 months (responders only).

Patients who discontinue cyclosporine before 6 months, should continue eltrombopag treatment until 6 months.

Patients who discontinue both eltrombopag and cyclosporine before 6 months or discontinue cyclosporine during the additional 18 months follow-up (responders only) should be scheduled for an end of study treatment visit as soon as possible after the last dose of study treatment

(eltrombopag and cyclosporine), at which time all the assessments listed in the visit evaluation schedule (under EOT) will be performed ([Table 7-2](#)). At a minimum, all patients who discontinue eltrombopag and/or cyclosporine (premature discontinuation, with patients no longer being in the study), including those who refuse to return for a final visit, will be contacted for safety evaluations during the 30 days following the last dose of study treatment.

The investigator must also contact the IRT to register the patient's discontinuation from study treatment.

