2.6.2 Duration of hematologic response

The time from start of the first hematologic response (the initial assessment, not the confirmatory assessment, of either CR or PR whichever occurs first by 6 months) to the date of first relapse will be derived as:

- Duration of first hematologic response (days) = End date (Date of first relapse) – start date of first hematologic response + 1

Longest duration will also be presented:

- Longest duration of hematologic response (days) = End date (Date of relapse) – start date of longest hematologic response + 1

Relapse is defined as no longer meeting the definition of PR (and not CR).

The duration of hematological response will be estimated using Kaplan-Meier method and the median time to relapse will be presented along with 95% confidence interval. If no relapse occurs, the patient will be **censored** at the date of last contact.

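### Duration of response is censored at last contact of any kind, not at the last blood count that could show relapse, which biases the Kaplan-Meier curve upward

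*SAP*

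**What the plan says.** The rule appears in two places in the SAP, and they agree. Section 2.1.3: "The last contact date will be used for censoring of patients in the analysis of duration of hematological response". Section 2.6.2: "If no relapse occurs, the patient will be censored at the date of last contact".

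Table 2-1 sets last contact as the latest complete date among several sources. These include "Date of withdrawal of consent", the disposition date, drug records (zero doses allowed), any collected sample including PK, any assessment with one non-missing value (a weight is enough), and "Start/End dates of AEs, medications or surgeries".

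The event is defined differently. Under SAP 2.6.2, relapse means no longer meeting the partial-response definition. Under SAP 2.5.1, that definition uses only neutrophil, platelet and reticulocyte counts.

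Protocol 10.5.1 names the Kaplan-Meier method but gives no censoring date, so the SAP wording alone sets the rule. No sensitivity analysis uses another date.

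**The concern.** Kaplan-Meier assumes that everyone in the risk set at a given time could be observed to fail at that time. Here an event needs a blood count, but staying at risk needs only a contact. Each responder who leaves without relapse adds event-free time for a stretch in which relapse could not have been recorded. This enlarges the denominators of later relapse steps and never adds an event.

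The documents make such a gap likely:

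- Under Protocol 7.1.5, patients who discontinue, including those who refuse a final visit, "will be contacted for safety evaluations during the 30 days following the last dose of study treatment".
- Protocol 6.3.3 follows patients stopped for an adverse event weekly for 4 weeks and then about every 4 weeks until resolution or stabilization. Protocol 8.1.1 follows events until resolved or judged permanent. Adverse-event end dates count as contact, so gaps beyond 30 days can occur.
- After month 6 the counts are local. Protocol 7.2.2.5.1 requires the four efficacy parameters at each scheduled visit, but the title of Table 7-5 describes these tests as potentially collected under local standard of care.

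Duration of response is listed among the key secondary objectives in Protocol 10.5.1. The trial is single-arm, so no comparator shares the bias. Responders who leave early contribute most of it.

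**Working it through.** The documents give no figure for duration of response, so there is none to reproduce.

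**Inputs from the documents.** Visits are every 4 weeks from month 9 to month 24 (Protocol 7.1), taken as a 28-day grid. The safety contact runs to 30 days after last dose (Protocol 7.1.5). A relapse proportion of 35% is the protocol's figure for responders to h-ATG and cyclosporine (Protocol 2.1), borrowed here as an assumption.

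**Other assumptions.** 50% relapse as a second case; early dropout of 0, 10, 30 or 50%; gaps of 90 and 180 days; follow-up of 644 days (about 21 months) from response; exponential relapse and dropout.

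**Hand calculation.** Let λ be the relapse hazard, μ the dropout hazard and g the gap. Once g days have passed, the patients retained without data, as a fraction of those truly under observation, are

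f = μ(e^((λ+μ)g) − 1)/(λ+μ),

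and the estimated hazard is λ/(1+f). With 35% relapse and 30% dropout over 644 days:

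- λ = −ln(0.65)/644 = 0.000669 per day; μ = −ln(0.70)/644 = 0.000554 per day.
- g = 30: f = 0.0169; the estimate is 0.65^(1/1.0169) = 0.655 against a true 0.650, a rise of 0.5 points.
- g = 90: f = 0.0527; the estimate is 0.65^(1/1.0527) = 0.664, a rise of 1.4 points.

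**Simulation.** Relapse was detectable only at the 28-day visits. The same data were censored at the last count and then at discontinuation plus g. Censoring at the last count recovered the true curve (0.65 against 0.65). Rise in 21-month relapse-free probability under last-contact censoring, in percentage points:

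| Relapse | Dropout | 30-day gap | 90-day gap | 180-day gap |
|---|---|---|---|---|
| 35% | 0% | 0.0 | 0.0 | 0.0 |
| 35% | 10% | 0.1 | 0.4 | 0.8 |
| 35% | 30% | 0.5 | 1.4 | 2.5 |
| 35% | 50% | 0.9 | 2.6 | 4.7 |
| 50% | 30% | 0.6 | 1.7 | 3.3 |
| 50% | 50% | 1.1 | 3.3 | 6.2 |

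A second simulation assumed 30% or 50% relapse and 20% or 40% dropout by 18 months. Estimated relapse at day 600 fell as follows:

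| Relapse, dropout | Censored at last count | 30 days later | 90 days later |
|---|---|---|---|
| 30%, 20% | 0.324 | 0.321 | 0.315 |
| 30%, 40% | 0.324 | 0.317 | 0.304 |
| 50%, 20% | 0.531 | 0.526 | 0.518 |
| 50%, 40% | 0.531 | 0.521 | 0.502 |

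The falls are 0.3 to 1.0 points at 30 days and 0.9 to 2.9 points at 90 days.

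**At trial size.** With 25 responders (assumed), 35% relapse, 30% dropout and a 30-day gap, the mean upward shift at 21 months was 0.5 points (95th percentile 1.3). The sampling standard deviation was about 10 points. The shift was never negative in any replicate.

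**The case against.** The strongest objection is size. The only routine post-treatment contact is at 30 days. At that gap the shift is about a twentieth of a sampling standard deviation (0.5 against 10 points), on a descriptive endpoint with no test attached. That stands, and it limits the weight of the point. The 90- and 180-day gaps are scenarios, not documented intervals, although the adverse-event follow-up rules make gaps beyond 30 days foreseeable.

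The gap may also be shorter than assumed. Patients who stop treatment are due an end-of-treatment visit, and a count may be taken at the 30-day visit. The hematology rows of Protocol Table 7-2 are not legible in the available text, so this cannot be settled. It would not help for patients who refuse to attend.

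The SAP has safeguards. The cut-off date cannot serve as last contact unless the patient was seen or contacted that day, fully imputed dates are barred (2.1.3), and data after consent withdrawal are excluded (2.1.1). These block the worst over-crediting but leave the gap between last count and last contact open.

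Other durability outputs do not use this date: relapse rate (2.6.3) is a simple proportion, and response at 12 and 24 months (2.6.1) uses the full analysis set. At 35% relapse the median may not be reached under either rule. SAP 6.3.2 nevertheless plans Kaplan-Meier estimates at specific time points, and those are affected.

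Finally, the primary report is already written and secondary results are cumulative, so replacing the rule could make the two reports differ. That is a good reason to keep the current rule as a sensitivity analysis.

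**Conclusion.** The concern holds. The plan credits relapse-free time during which relapse could not be observed, and the resulting bias in the Kaplan-Meier curve can only be upward. Under the current visit schedule with a 30-day gap, the likely size is about 0.1 to 1 percentage point at 21 months. It grows to several points only with long gaps or many early departures. These figures rest on assumed relapse and dropout rates, exponential times, and no count during the gap. Patients who complete month 24 add little, because their extra time falls at the tail of the curve. The primary response rate and its success rule are untouched. The correction is worth making because the error is systematic, its size depends on dropout, and the remedy is cheap.

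**What to change.** In SAP 2.6.2, and in the matching sentence of 2.1.3, replace the date of last contact with the date of the last scheduled visit, on or before the cut-off, that has enough valid parameters to judge partial or complete response. Keep last contact date for its other uses. Retain last-contact censoring as a sensitivity analysis for continuity with the primary report.

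Two details need wording. First, say what makes a visit evaluable when a recent transfusion invalidates the platelet count. Excluding such visits moves censoring earlier for patients who may be losing response, which could itself be informative. Second, note that "The last contact date will be derived for patients not known to have died at the analysis cut-off date", so a responder who dies without relapse has no defined censoring date at present. The new date can be derived for such patients, but whether death ends a response is a separate decision.

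The cost is one sentence and one derived date. The estimate may become slightly less favourable and may differ a little from the primary report. SAP Section 1 describes the final analysis as still to be done, so the change can be documented before those results.
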